12.2.5 Treatment Related Adverse Events

These will be defined for each arm using CTCAE v 4.0 criteria.

12.2.6 Health-Related Quality of Life

The EORTC-QLQ-C-30 is one of the most commonly used QoL instruments in oncology studies and has been assessed in previous studies evaluating health related quality of life in patients with head and neck cancer. It is a 30 item instrument comprising six functional scales (physical functioning, cognitive functioning, emotional functioning, social functioning, role functioning, and global quality-of-life) as well as nine symptom scales (fatigue, pain, nausea/vomiting, dyspnea, insomnia, appetite loss, constipation, diarrhea, and financial difficulties). Except for overall health status and global quality of life items, responses for all items are 4-point categorical scales ranging from 1 (not at all) to 4 (very much). The overall health/quality of life responses are 7 point Likert scales.

The questions on the EORTC-QLQ-C30 will be scaled and scored using the recommended EORTC Quality of Life Group procedures. Raw scores will be transformed using a linear scale ranging from 0 to 100, with a higher score representing a higher level of functioning or a higher level of symptoms. Clinical significance will be defined as differences of at least 10 points (on a 0-100 scale). For example, a mean increase of ≥ 10 points on a functional scale would indicated a moderate improvement, whereas a mean decrease of ≥ 10 points would be interpreted as moderate worsening.

12.3 EXPLORATORY END POINTS:

12.3.1 Baseline PD-L1 Expression on Tumor Cells

Fresh biopsies will be provided for biomarker analysis if accessible and deemed safe and clinically necessary by the investigator. An archived biopsy of metastatic or loco-regionally recurrent disease obtained prior to therapy is acceptable if the fresh biopsy is not clinically indicated. If neither fresh nor archived material are available from recurrent/metastatic site, archived material from the primary disease at diagnosis is allowable with permission of PI. On-treatment biopsies are not required.

Expression of PD-L1 expression on tumor cells will be assessed using an automated immunohistochemical assay developed by BMS and Dako. PD-L1 positivity will be defined as at least 5% of tumor cells showing cell surface PD-L1 staining of any intensity in a section containing at least 100 tumor cells that could be evaluated. Expression of PD-L2 expression on tumor infiltrating lymphocytes (TILs) may also be assessed. Additional IHC studies may be conducted evaluating CD4, CD8, FOXP3, HLA Class I,

Antigen Presenting Machinery (APM), and HPV oncoproteins expression. PD-L1 IHC will be conducted by BMS (see appendix for additional information)

12.3.2 Peripheral Blood Mononuclear Cells Composition (PBMCs)

Peripheral blood samples will be taken prior to initiation of study therapy and at designated time points. Ideally, peripheral blood samples should be used for immunophenotyping or characterization of the immune cell subsets in the periphery, including, but not limited to, T cells, B cells, NK cells, or subpopulations of the aforementioned immune cell types. These samples may also be used to assess immune cell function or antigen specific T cell proliferation.

12.3.3 Serum Biomarkers

Blood samples for exploratory serum biomarker analysis will be drawn at the time points indicated. Blood samples will be processed to collect serum and then put in frozen storage. Samples may be assessed by ELISA, seromics and/or other relevant multiplex based protein assay methods for immune or HNSCC-related factors that will predict for Nivolumab and/or Nivolumab+SBRT benefit. Although numerous potential serum-based biomarkers are under investigation, we will look at soluble PD-1 and PD-L1. However, other biomarkers may be of interest and future analyses may include them.

12.3.4 Neo Antigen Expression (optional)

Neo-epitope analysis using whole exome sequencing may also be conducted on baseline biopsy specimen and evaluated as a predictor of response to therapy.

13.1 CRITERIA FOR REMOVAL FROM STUDY

Treatment with Nivolumab will continue until RECIST 1.1-defined progression, unacceptable toxicity, failure to obtain PI approval for radiation plans that exceed normal tissue dose constraints as outlined in the appendix, or withdrawal of consent.

13.2 Discontinuation Criteria for Nivolumab

Treatment should be permanently discontinued for the following:

- Any Grade 2 drug-related uveitis or eye pain or blurred vision that does not respond to topical therapy and does not improve to Grade 1 severity within re-treatment period OR requires systemic treatment.
- Any Grade 3 non-skin, drug related adverse event lasting > 7 days with the following exceptions for drug-related laboratory abnormalities, uveitis, pneumonitis, bronchospasm, neurologic toxicity, hypersensitivity reactions, and infusion reactions;
 - Grade 3 drug-related uveitis, pneumonitis, bronchospasm, neurologic toxicity, hypersensitivity reaction, or infusion reaction of any duration requires discontinuation.
 - Grade 3 drug-related laboratory abnormalities do not require treatment discontinuation except:
 - Grade 3 drug-related thrombocytopenia > 7 days or associated with bleeding requires discontinuation.

- Any drug related LFT abnormality that meets the following criteria require discontinuation;
 - AST or ALT > 8x ULN
 - Total bilirubin > 5x ULN
 - Concurrent AST or ALT > 3 x ULN and total bilirubin > 2 x ULN.
- Any grade 4 drug-related adverse event or laboratory abnormality, except for the following events which do NOT require discontinuation:
 - Isolated grade 4 electrolyte imbalances that are not associated with clinical sequelae and are corrected with supplementation/appropriate management within 72 hours of their onset.
 - Isolated grade 4 electrolyte imbalances that are not associated with clinical sequelae and are corrected with supplementation within 72 hours of their onset.
- Any dosing delays lasting > 6 weeks with the following exceptions:
 - Dosing delays to allow for prolonged steroid tapers to manage drug-related adverse events are allowed. Prior to reinitiating treatment in a subject with a dosing delay lasting > 6 weeks, the primary investigator must be consulted. Tumor assessments should continue as per protocol even if dosing is delayed.
 - Dosing delays > 6 weeks that occur for non-drug related reasons may be allowed if approved by the primary investigator. Prior to reinitiating treatment in a subject with a dosing delay lasting > 6 weeks, the primary investigator must be consulted. Tumor assessments should continue as per protocol even if dosing is delayed.
- Any adverse event, laboratory abnormality, or intercurrent illness which, in the judgement of the investigator, presents a substantial clinical risk to the subject with continued Nivolumab dosing.

13.3 Treatment Beyond Disease Progression with Nivolumab

Accumulating evidence indicates a minority of subjects treated with immunotherapy may derive clinical benefit despite initial evidence of progressive disease (PD). Subjects will be permitted to continue on treatment with Nivolumab beyond initial RECIST 1.1 PD as long as they are meeting the following criteria:

- Investigator-assessed clinical benefit without rapid disease progression.
- Tolerance of study drug
- Stable performance status
- Treatment beyond progression will not delay an imminent intervention to prevent serious complications of disease progression (e.g. CNS metastases)
- Subject provides written informed consent prior to receiving any additional nivolumab treatment, using an ICF describing any reasonably foreseeable risks or discomforts, or other alternative treatment options.

The assessment of clinical benefit should take into account whether the subject is clinically deteriorating and unlikely to receive further benefit from continued treatment.

All decisions to continue treatment beyond initial progression must be discussed with the primary investigator and documented in the study records. Subjects will be re-consented with an ICF describing any reasonable foreseeable risks or discomforts.

Subjects should discontinue study therapy upon further evidence of progression, defined as an additional 10% or greater increase in tumor burden volume from time of initial progression.

New lesions are considered measurable at the time of initial progression if the longest diameter is at least 10mm (except for pathological lymph nodes, which must have a short axis of at least 15mm). Any new lesion considered non-measurable at the time of initial progression may become measurable and therefore included in the tumor burden measurement if the longest diameter increases to at least 10 mm (except for pathological lymph nodes which must have an increase in short axis to at least 15mm).

For statistical analyses that include investigator assessed progression date, subjects who continue treatment beyond initial investigator-assessed RECIST 1.1 defined progression will be considered to have investigator-assessed progressive disease at the time of the initial progression event. Responses beyond this 1st progression event will not be counted towards the primary endpoint of overall response rate.

Patients who have initial progression who are deemed eligible and decide to continue Nivolumab therapy will continue to have study mandated scans per Section 10.1 until further progression or 96 weeks, whichever occurs first.

14.0 BIOSTATISTICS

11.1 Primary Objective

The primary objective of this study is to compare best overall response (BOR) rate by 96 weeks as determined by the investigator using RECIST 1.1 criteria between patients receiving Nivolumab and SBRT and those receiving Nivolumab alone. BOR rate is defined as the number of patients randomized to a given arm with a best overall response of complete response (CR) or partial response (PR) of non-irradiated lesions divided by the total number of patients randomized to the given arm. In order to ascertain this endpoint, efforts will be made so that patients will be followed for 96 weeks or until progression of disease (and treatment cessation), whichever comes first.

Based upon an estimated ORR of 15% in a PD-L1 unselected population in the Nivolumab alone arm (based on data from Siewert, et al; see background) and an ORR of 45% in the Nivolumab and SBRT arm, the enrollment of 54 patients with a two-sample proportion test will provide a one-sided alpha of 0.10 and a power of 0.80. Assuming a 10% drop-out rate, we will enroll a total of 60 patients. Patients will be randomized to the two treatment arms in a 1:1 ratio. Patients will be stratified based upon viral status (virus negative versus virus positive; virus status is defined by EBV (EBER testing) or HPV (p16, HPV ISH, HPV PCR) testing). Assuming a constant enrollment of 3 subjects per month, it would take approximately 20 months to randomize 60 patients. Calculations were completed using software R 3.1.1 and EAST 6.

To ensure eligible endpoints are well defined, a minimum of 6 months of follow up after treatment initiation is required. Patients lost to follow-up prior to 6 months (24 week scan) will be replaced, regardless of response. Patients lost to follow-up between 6 months and 24 months will be included in the ORR calculation.

Secondary objectives:

OS and PFS will be evaluated by the regular survival analysis tools such as Kaplan-Meier and competing risks methods. Comparisons will be conducted between the two arms by the stratified log-rank test and Gray's test.

The DOR will be calculated from the time of response to progression or last follow up and analyzed using the Kaplan-Meier method among patients who showed response.

All tr-AEs will be tabulated and summarized. The cumulative incidence of all tr-AEs and Grade 3+ tr-AEs, etc., will be compared between the two arms by using Gray's test. For this analysis all randomized subjects who received at least one dose of study drug will be included.

The questions on the HRQOL will be scaled and scored using the recommended EORTC Quality of Life Group procedures. Raw scores will be transformed using a linear scale ranging from 0 to 100, with a higher score representing a higher level of functioning or a higher level of symptoms. Wilcoxon rank sum tests will be conducted to compare the scores across the two arms and longitudinal plots will be made to visually examine the pattern of change of scores at each specified time point. If appropriate, an exploratory linear mixed model will also be used to incorporate correlations among various time points, and include additional variables such as interaction between treatment and number of assessments, site of the primary tumor, baseline score, and performance status.

Because the toxicity of Nivolumab combined with SBRT is unclear, we will utilize an interim stopping rule for Arm 2 based on the first 20 randomized to this arm to protect later patients from unacceptably high toxicity rate. Using data from recently reported early phase trials of Nivolumab in NSCLC, we view 14% as an acceptable rate of acute (within 3 months of study initiation) \geq Grade 3 treatment-related adverse events; an unacceptable rate of acute \geq Grade 3 treatment-related adverse events is 30%. If more than 5 (e.g. 6 or more) of the first 20 patients experience an acute \geq Grade 3 treatment-related adverse event, the trial will be stopped early. If the true toxicity rate is 30%, the above boundary assures a 58% probability of stopping the trial at interim analysis; if the true toxicity rate is 40%, there is an 87% chance of stopping the trial early. If the true toxicity rate is 14%, the above boundary has only a 5% probability of stopping the trial early. Of note, for radiation dermatitis, only Grade 4 treatment-related adverse events will be included in the interim analysis.

For the exploratory objectives, all lab measurements will be summarized and descriptive statistics will be provided. When correlation between lab measurements and treatment outcomes are of interest, Wilcoxon rank sum tests will be conducted to examine the difference between responders and non-responders within each arm. An exploratory multivariate logistic regression analysis to determine whether, once adjusted for relevant clinical covariates and treatment arm, tumor PD-L1 or serum immunophenotypic changes predict for response to Nivolumab.

To clarify we define population for the above analyses

- Randomized subjects for ORR analysis: all enrolled subjects who were randomized and provided at least 6 months of follow-up after treatment initiation. This is the dataset for the primary objective and irORR.
- All randomized subjects: all enrolled subjects who were randomized. This is the dataset for baseline demographics and time-to-event endpoints (PFS, OS).
- Treated subjects: all randomized subjects who received at least one dose of study drug. This is the dataset for safety evaluation. For instance, if a subject receives a single dose of Nivolumab but withdraws from study prior to the first dose of radiation, that subject will be considered treated.
- Biomarker Subjects: all randomized subjects with available biomarker data.
- PRO subjects: all subjects with available Patient Reported Outcomes (PRO) data.

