3.3.3 Nivolumab Efficacy and Safety

In our own trial, we will use Nivolumab as the anti-PD-1 agent. Nivolumab is a fully human monoclonal immunoglobulin IgG4 antibody that binds to PD-1 cell surface membrane receptor. A recently reported on Phase I open label, multiple dose escalation study investigated the safety and efficacy of Nivolumab in 304 patients with melanoma, renal cell carcinoma, non-small cell lung carcinoma (NSCLC), colorectal cancer, or hormone refractory prostate cancer [18]. Squamous NSCLC is the histology most biologically similar to HNSCC. For NSCLC, the most active doses were 3 and 10 mg/kg, with a reported ORR of between 19% and 26%, with durable responses observed in both

squamous and non-squamous subtypes. There was no maximally tolerated dose identified in the above Phase I trial. Drug-related adverse events occurring in >5% of subjects included, in order of most frequent to least frequent: fatigue, rash, diarrhea, pruritus, nausea, decreased appetite, decreased hemoglobin, and pyrexia. Approximately 15% of patients experienced Grade 3 or 4 adverse events. Those occurring in greater than >1% of research subjects included: fatigue (1.6%), lymphopenia (1.3%), abdominal pain (1%), diarrhea (1%), hypophosphatemia (1%) and pneumonitis (1%). Approximately 49% of patients on the Phase I study experienced a severe adverse event (SAE); 7.6% of patients experienced a Grade 3-4 SAE. Drug-related SAEs occurred in 11.5% of patients. Grade 3-4 SAEs that occurred in 2 or more study subjects included: diarrhea (1%), pneumonitis (1%), pneumonia (0.7%), and increased lipase (0.7%). Only 5.9% of patients had their treatment discontinued because of an SAE. These SAEs included pneumonitis (4 subjects) and hepatitis (2 subjects). There were 3 treatment-related deaths (1%), all related to pneumonitis.

Siewert, et al recently updated their experience with Pembrolizumab (MK-3475) in an unselected group (both PDL1 positive and negative) of patients with recurrent/metastatic HNSCC. In this expansion cohort of KEYNOTE 012, ORR (confirmed and unconfirmed) per RECIST 1.1 was 18.2% (95% CI, 11.1-27.2) [19].

3.4 Rationale for and Safety of Combining Nivolumab with Stereotactic Body Radiation Therapy (SBRT)

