4.1 OVERVIEW OF STUDY DESIGN/INTERVENTION

4.2 Design

This is a randomized (1:1), open label Phase 2 screening trial in subjects ≥ 18 years old with metastatic HNSCC. Subjects will stratified based on viral status (p16+ OPC/EBER+ NPC vs others) and then randomized to either Nivolumab with interdigitated SBRT or Nivolumab alone.

Subjects must undergo screening evaluations to determine eligibility within 28 days prior to randomization.

Sixty (60) subjects will be randomized to one of the following arms:

- Arm 1: Nivolumab 3mg/kg IV every 2 weeks
- Arm 2:
 - Image Guided, Stereotactic Body Radiotherapy (27 Gy over 3 fractions given every other day) to a single lesion to start by study day 14 (study day 1 is day of first dose of Nivolumab).
 - Nivolumab 3mg/kg IV starting day 1 and then every 2 weeks thereafter.
- Treatment with Nivolumab will continue until progression or unacceptable toxicity.

Key Inclusion Criteria:

- 1) Males and females ≥ 18 years of age.
- 2) Eastern Cooperative Oncology Group (ECOG) performance status ≤ 2 .
- 3) Histologically confirmed metastatic HNSCC, including nasopharynx WHO Type I-III histologies; patients can have simultaneous loco-regional disease.
- 4) Subjects must have at least two lesions:
 - One lesion must be safely amenable to irradiation in the opinion of the treating radiation oncologist. This can be a lesion that was previously irradiated as long as prior radiation preceded projected first fraction of SBRT by at least 6 months.
 - At least one, not-to-be-irradiated lesion measurable by CT or MRI per RECIST 1.1 criteria.
- 5) Available formalin fixed, paraffin-embedded (FFPE) tumor tissue block with unstained slides of tumor sample obtained via excisional, incisional, or core needle biopsy from a loco-regionally recurrent or metastatic lesion; FFPE tumor tissue block with unstained slides from the primary disease is acceptable with approval of principal investigator.
- 6) Documentation of tumor viral status (p16 testing for oropharynx, EBER for nasopharynx). Tests done on primary tumor specimens at outside institutions are sufficient to meet this criterion.
- 7) Prior palliative or curative radiotherapy must be completed at least 14 days prior to randomization.

Key Exclusion Criteria:

- 1) Active brain metastases or leptomeningeal metastases are not allowed.
- 2) Non-squamous histologies are not allowed; an exception is made for WHO Type I-III nasopharynx histologies.

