12.1.10 Verification Scans

- Verification of Response: confirmation of response (CR or PR) is required. Confirmed CR or PR will be claimed only if the criteria for each are met at a subsequent time point (minimum 4 weeks after criteria for an objective response are first met).
- Verification of Progression: progression of disease should be verified in cases where progression is equivocal. If repeat scans confirm PD, then progression should be declared using the date of the initial scan. If repeat scans do not confirm PD, then the subject is considered not to have progressive disease per RECIST 1.1.

Table 3 – Best overall response when confirmation of CR and PR required.

Overall response First time point	Overall response Subsequent time point	BEST overall response
CR	CR	CR
CR	PR	SD, PD or PR ^a
CR	SD	SD provided minimum criteria for SD duration met, otherwise, PD
CR	PD	SD provided minimum criteria for SD duration met, otherwise, PD
CR	NE	SD provided minimum criteria for SD duration met, otherwise NE
PR	CR	PR
PR	PR	PR
PR	SD	SD
PR	PD	SD provided minimum criteria for SD duration met, otherwise, PD
PR	NE	SD provided minimum criteria for SD duration met, otherwise NE
NE	NE	NE

CR = complete response, PR = partial response, SD = stable disease, PD = progressive disease, and NE = inevaluable.

^a If a CR is truly met at first time point, then any disease seen at a subsequent time point, even disease meeting PR criteria relative to baseline, makes the disease PD at that point (since disease must have reappeared after CR). Best response would depend on whether minimum duration for SD was met. However, sometimes 'CR' may be claimed when subsequent scans suggest small lesions were likely still present and in fact the patient had PR, not CR at the first time point. Under these circumstances, the original CR should be changed to PR and the best response is PR.

12.2 Secondary End Points:

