15.3 Randomization

Patients will be randomized to the Nivolumab and SBRT arm or Nivolumab only arm. For patients enrolled, immediately after consent is obtained, the RSA at MSKCC will register participants in the Protocol Participant Registration (PPR) system. Once the participant's eligibility is established the registration will be finalized and the participants will be randomized using the Clinical Research Database (CRDB). Randomization will be accomplished by the method of random permuted block, and will be stratified by viral status (positive or negative). After treatment arm is determined by randomization, RSAs will notify the physicians at MSKCC of the treatment arm and participant ID via email within 24 hours of randomization. All Data will be collected and analyzed at MSKCC. Compiled data will be submitted to the biostatistician on study ([name]) for analysis.

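### The primary ORR test should be named as a one-sided exact unconditional (Boschloo) test: the present wording covers forms that either leave alpha unused or exceed it

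*Combined protocol and SAP*

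**What the plan says.** The only text that names a test for objective response is in Section 14.0 (Biostatistics), under the primary objective: "the enrollment of 54 patients with a two-sample proportion test will provide a one-sided alpha of 0.10 and a power of 0.80". The assumed rates are 15% with nivolumab alone and 45% with nivolumab plus SBRT, randomised 1:1. The total is then raised for losses: "Assuming a 10% drop-out rate, we will enroll a total of 60 patients". Section 4.2 repeats these design figures without naming a test, and the definition of the ORR analysis set at the end of Section 14.0 adds none. R 3.1.1 and EAST 6 are cited for the calculations, but no procedure is identified.

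Other endpoints are specified more closely. For OS and PFS, "Comparisons will be conducted between the two arms by the stratified log-rank test" and Gray's test. For quality of life, Wilcoxon rank sum tests. Section 15.3 says that randomisation "will be stratified by viral status (positive or negative"). Nothing says whether the strata enter the ORR test.

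Three further points bear on the analysis:

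- **Losses before 6 months:** "Patients lost to follow-up prior to 6 months (24 week scan) will be replaced, regardless of response".
- **Setting:** Section 4.2 states "This is a randomized (1:1), open label Phase 2 screening trial", and response is assessed by the investigator.
- **Confirmation:** Section 12.1.10 states that "confirmation of response (CR or PR) is required".

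**The concern.** A two-sample proportion test is a family of tests. At about 30 patients per arm its members differ enough to change the conclusion. The pooled z-test without correction, the continuity-corrected z, Fisher's exact test and the exact unconditional tests all fit the wording, but they differ in true size and in power.

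Two things are at stake. First, one admissible form does not hold the alpha that the plan states. Second, the form that reproduces the planned sample size uses only part of that alpha, so power already paid for in patients is left unused. In an open-label trial with investigator-assessed response, a test fixed in writing also removes any later question about how it was chosen.

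**Working it through.** **Inputs.** From Section 14.0: p1 = 0.15, p2 = 0.45, one-sided alpha 0.10, power 0.80, 1:1 allocation, 54 patients raised to 60. From Section 4.2: 30 per arm at full enrolment.

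**Step 1: reproduce the plan's figure.** With z(0.90) = 1.2816, z(0.80) = 0.8416, d = 0.30 and mean rate 0.30:

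- Uncorrected: n = [1.2816·√(2·0.30·0.70) + 0.8416·√(0.15·0.85 + 0.45·0.55)]² / 0.30² = (0.8305 + 0.5154)² / 0.09 = 20.1. That is 21 per arm, 42 in total.
- Continuity-corrected: (n/4)·[1 + √(1 + 4/(n·d))]² = (20.13/4)·[1 + √(1 + 4/6.04)]² = 26.4. That is 27 per arm, 54 in total.
- Losses: 54/0.90 = 60.

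The corrected formula gives exactly 54. An uncorrected formula at two-sided 0.10 gives 28 per arm (56 in total, with power 0.790 at 27 per arm), but it contradicts the stated one-sided alpha. The corrected z, or Fisher, is therefore the form implied by the sample size. The two have identical rejection regions at 27 and at 30 per arm.

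**Step 2: exact size and power.** For a rejection region R, power is the sum over (x1, x2) in R of Bin(x1; n1, 0.15)·Bin(x2; n2, 0.45). Size is the same sum with a common rate p. The maximum is taken over 1,999 values of p from 0.0005 to 0.9995. Boschloo uses the Fisher p-value as its statistic and takes the largest cut-off that keeps maximum size at or below 0.10 (0.1355 at 27 per arm, 0.1395 at 30).

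| Per arm | Test | Size at 15% | Maximum size | Power |
|---|---|---|---|---|
| 27 | Fisher = corrected z | 0.052 | 0.067 | 0.807 |
| 27 | Boschloo | 0.073 | 0.097 | 0.872 |
| 27 | Uncorrected z | 0.104 | 0.118 | 0.886 |
| 30 | Fisher = corrected z | 0.055 | 0.078 | 0.856 |
| 30 | Boschloo | 0.075 | 0.097 | 0.906 |
| 30 | Uncorrected z | 0.107 | 0.122 | 0.915 |

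Before rounding, the gain over Fisher is 0.8721 − 0.8066 = 6.6 points at 27 per arm and 0.9063 − 0.8562 = 5.0 points at 30. The 30-per-arm rows are the more relevant, because early losses are replaced.

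**Step 3: what this means for a result.** With 4 responders on nivolumab alone (27 or 30 per arm), the SBRT arm needs 10 responders under Fisher, 9 under Boschloo and 8 under the uncorrected z. At the design rates, the uncorrected z is positive and Fisher negative in 7.9% of trials with 54 patients and 5.9% with 60.

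**Step 4: unequal arms.** The ORR set requires at least 6 months of follow-up, so equal arms are not assured.

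| Control/SBRT | Fisher power | Boschloo power | Gain (points) |
|---|---|---|---|
| 31/29 | 0.867 | 0.895 | 2.8 |
| 29/31 | 0.856 | 0.897 | 4.1 |
| 28/26 | 0.829 | 0.880 | 5.0 |

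In every split run, Boschloo's maximum size stayed below 0.10 and its rejection region contained Fisher's. At 28/26, 29/28 and 31/29 the maximum size of the uncorrected z was 0.125 to 0.132. The counts in Step 3 also shift: at 31/29 with 4 control responders, Fisher needs 9, and Boschloo and the uncorrected z both need 8.

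**Step 5: control-rate sensitivity.** In the pembrolizumab cohort described in Section 3.3.3, "ORR (confirmed and unconfirmed) per RECIST 1.1 was 18.2% (95% CI, 11.1-27.2"). At 18.2% against a fixed 45%, Fisher has power 0.713 (54) or 0.773 (60), and Boschloo 0.799 or 0.838. If the 30-point difference is kept (48.2%, an assumption), Fisher has 0.792 or 0.846, and Boschloo 0.862 or 0.892.

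**The case against.** The strongest reply is that nothing in the plan is wrong. It states a test family, alpha, rates, N and power. The form that reproduces 54 patients holds alpha and delivers 0.807, and with 60 analysed Fisher already has 0.856. On this view the gap is one missing word, and preferring Boschloo to Fisher is a matter of taste.

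Much of this stands. A reader might infer that the sample size is in error; Step 1 shows that it is not. A reader might also take 0.807 as the planned test's power and say that the plan forfeits 6.6 points. The documents do not support that, because the Fisher baseline is inferred and the gain shrinks when the arms differ. If an uncorrected z was intended, Boschloo lowers power by about 1 to 2 points and its benefit is control of alpha. The alpha excess is also modest for a screening trial: 0.104 and 0.107 at a 15% common rate with equal arms, with the maxima at rates of about 6% (27 per arm) and 50% (30 per arm).

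The 18.2% rate might be read as showing that the trial is underpowered. It does not. It counts unconfirmed responses, whereas this trial requires confirmation. It comes from a different anti-PD-1 agent. And the shortfall arises partly from holding 45% fixed, which narrows the difference to 26.8 points. It is a sensitivity check only.

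The charge of mere preference fails. In every split run, Boschloo rejects whenever Fisher does and in further tables too, while size stays below 0.10. It is the more powerful test at the same stated alpha.

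**Conclusion.** The point holds as a specification gap with a concrete, better option. The wording leaves open a form whose maximum size is 0.118 to 0.122 with equal arms. The form implied by the sample size has maximum size only 0.067 to 0.078. Boschloo lies between them: maximum size 0.097, and power 0.872 (54) or 0.906 (60) with equal arms. Its gain over Fisher is 6.6 and 5.0 points with equal arms, and about 3 to 5 points in slightly unequal splits.

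These figures assume 15% against 45%, one-sided 0.10 and an unstratified test. The Fisher baseline is an inference from the sample-size formula.

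Two stronger readings are not supported. Because the trial is open label, a reader might infer that the test will be chosen after the data are seen; no passage says so. Nor does the silence on viral status cost power: stratifying is not the source of the gain, so it is an optional match to the randomisation.

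**What to change.** Before any comparison of response by arm, add a sentence to Section 14.0 stating that the primary ORR comparison will use a one-sided exact unconditional (Boschloo) test at alpha 0.10, computed with the actual arm sizes. Keep the 54/60 patients and the 15% and 45% assumptions. Report the named test's power: 0.872 at 27 per arm and 0.906 at 30. Say in the same place whether viral status enters the test; either answer is acceptable.

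If a more familiar test is preferred, name Fisher explicitly. It holds alpha, with power 0.807 (54) or 0.856 (60). The uncorrected z should not be used.

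The cost is one sentence, with no added patients or visits. The unstratified test is in standard software; a stratified version would need a short program. The drawbacks are that the test is less familiar and that a late move away from the form that reproduces the sample size could look data-driven. The timing condition is therefore essential.
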